8.7.5 Continued Access to Study Drug

At AROG's discretion, patients receiving crenolanib at the time of study closure may continue to receive crenolanib until disease progression or initiation of other therapy. However, if a serious adverse event (SAE) occurs during this time, AROG may request additional information (such as local lab results, concomitant medications, and hospitalizations) in order to evaluate the reported SAE

8.8 Blinding

Protocol: ARO-004

This is an open-label study.

8.9 Concomitant Therapy

All supportive therapy for optimal medical care will be given during the study period at the discretion of the attending physician(s) within the parameters of the protocol and documented on source documents as concomitant medication.

No other anticancer therapy including immunotherapy, hormonal cancer therapy, or experimental medications other than hydroxyurea (which is allowed during the first two weeks) will be permitted while patients are participating in this study. Radiation therapy will not be allowed. No hematopoietic growth factors will be permitted while patients are participating in this study. Any disease progression requiring other forms of specific antitumor therapy will be cause for discontinuation of study therapy.

At the discretion of the investigator, crenolanib can be administered with standard anti-emetic and anti-diarrheal premedication. Prophylaxis can be discontinued if patient tolerates crenolanib without significant nausea and vomiting.

Donor lymphocyte infusion (DLI) will be permitted after 2 cycles (56 days) of crenolanib therapy exclusive of any drug hold for resolution of toxicity.

8.10 Treatment Compliance

Patient compliance with study medication will be assessed at each visit. Compliance will be assessed by counting returned tablets. Deviation(s) from the prescribed dosage regimen should be recorded in the CRF.

Definition of noncompliance: Patients who are significantly noncompliant will be discontinued from the study. A patient will be considered significantly noncompliant if he or she takes <60% of the total amount of expected study drug taken in a visit interval.

In addition, to monitor patient compliance during the two first cycles, patients will be asked to complete a diary to record the date, time, and amount (the number of tablets) of crenolanib taken (Appendix III).

The following procedures will be employed to assure appropriate drug accountability:

- Drug accountability will be emphasized at the start-up meeting.
- Drug accountability will be monitored throughout the study.
- Each patient should be instructed to return all study drug packaging and unused material to the study site at each visit. The study site personnel will keep a record of all drug dispensed to and returned by the patients throughout the study. Study site personnel will return or destroy (as requested) all used, unused, and expired study drug for all patients.

8.11 Sample Collection and Testing

Protocol: ARO-004

Appendix V lists the specific standard tests to be performed for this study.

8.11.1 Samples for Standard Laboratory Testing

Blood samples will be collected at the times specified in the Study Schedule (Appendix IV). Standard laboratory tests, including chemistry, liver function tests, and hematology panels, will be performed as outlined below.

- Cycle 1: labs twice weekly (at least 24 hours apart) for the first two weeks of cycle 1, then weekly (±3 days) for the second two weeks of cycle 1
- Cycle 2: labs every 14 days ±4 days
- Cycle 3 to Cycle 6: labs every 28 days ± 14 days
- Cycle 6 onwards: once every two cycles (± 1 cycle)

A pregnancy test should be performed at study entry and at any time during the study if clinically indicated by history or clinical exam. Other clinical laboratory tests will be analyzed by either a central or a local laboratory. Appendix V lists the specific tests that will be performed for this study.

Investigators must document their review of each laboratory safety report

8.12 Follow up Visits

The Study Schedule in Appendix IV lists the specific follow up visits for this study.

The Study Schedule applies to patients receiving study drug. The calendar should re-commence as start of cycle 1 when drug is resumed post allogeneic transplant. Patients who have discontinued study drug for any reason should be followed for survival.

8.13 Translational Research

Translational studies to be evaluated include but are not limited to:

- 1. Pharmacokinetic analysis (Pk)
- 2. Whole-blood phospho-flow cytometry to detect activation of FLT3 and other signal transduction molecules in leukemic blasts from patients
- 3. Plasma inhibitory assay to assess if therapeutically adequate concentrations of crenolanib were achieved in each patient (PIA)
- 4. Bone marrow aspirate samples

Bone marrow samples will be collected at the time of marrow sampling with 2 additional aspirations drawn and placed in heparinized tubes. These samples will be refrigerated and shipped at 4-8°C within 24 hours of collection to the laboratory specified in Appendix XII.

The participating institution will receive a laboratory kit containing blood collection tubes, labels, collection instructions from AROG for the collection of samples from consenting patients. Site should contact AROG (Appendix XIV)at to request a lab kit for each patient enrolled on the study.

Serum and blood for translational research will be obtained at multiple time points on Cycle 1, Day 1, a single trough level on Cycle 1 Day 2, at multiple time points on Cycle 1 Day 15, Cycle 2 Day 1 and Cycle 3 Day 1. Additional serum and blood samples for translational research may be drawn at the discretion of the investigator.

Sampling Strategy

On Day 1 of Cycle 1, serial blood samples for PK, whole blood phosphoflow, and PIA will be drawn for translational research at the following time points: pre dose and at 30 (\pm 10), 60 (\pm 15), 120 (\pm 15) minutes, 4 (\pm 1) hours, and 8 (\pm 2) hours after crenolanib administration (Appendix VIII forms).

On Day 2 of Cycle 1 (24 (± 6) hours), blood samples for Pk and PIA only will be drawn at a single time-point: **pre** first dose to obtain the trough levels of crenolanib. (Appendix VIII).

In order to obtain the 24 hour time point, all other day 1 dosing (2 doses) will be held. It is also crucial that the 24 hour time point be obtained prior to dose administration on day 2.

On Day 15 of cycle 1, samples for Pk, whole blood phosphoflow, and PIA will be drawn at the following time points: pre dose prior to ANY study drug ingestion for the day, then $30 (\pm 10)$ minutes, and $4 (\pm 1)$ hours after administration of first crenolanib dose. **Do not administer second or third dose of crenolanib until after 4 hour time point is obtained on day 15.** (Appendix IX forms).

On Day 1 of Cycle 2, and Day 1 of Cycle 3, samples for PK, whole blood phosphoflow, and PIA will be drawn at the following time points: pre dose prior to ANY study drug ingestion for the day, and 4 (± 1) hours after administration of first crenolanib dose. **Do not administer subsequent doses of crenolanib until after 4 hour time point is obtained.** (Appendix X forms).

For dose escalations, repeat the Day 1 of Cycle 1 and Day 15 of Cycle 1 instructions.

On subsequent courses, samples may be obtained at the discretion of the investigator (e.g., predose), and whenever possible every 2-4 cycles (Appendix X forms).

Optional bone marrow biopsy samples and concurrent whole blood samples may be collected at any time while the patient is on treatment, at the discretion of the investigator (Appendix X).

Sample Processing Instructions

See lab manual. Other Correlative Studies

Tissue cells will be banked for future correlative science research studies. Additional correlative science research may be performed at the discretion of the investigators or AROG, including assays for resistance studies for cases in which responses are noted but are not durable. But the total blood drawn for these studies will be less than 400ml in any month.

9. Response Definitions

9.1 Response Criteria

Response criteria will be adapted from the International Working Group for AML.²¹ Responders are relapsed/refractory patients receiving study drug as reinduction therapy who obtain a CR, CRi, or PR, with or without cytogenetic response, hematologic improvements, and morphologic leukemia-free state. Briefly, criteria are as follows:

- 1. Complete remission (CR):
 - a. Peripheral blood counts:
 - i. No circulating blasts
 - ii. Neutrophil count $\ge 1.0 \text{ x} 10^9/\text{L}$
 - 111. Platelet count $> 100 \times 10^9 / L$
 - b. Bone marrow aspirate and biopsy:
 - i. ≤5% blasts
 - ii. No Auer rods
 - iii. No extramedullary leukemia
- 2. Complete remission with incomplete blood count recovery (CRi):
 - a. Peripheral blood counts:
 - i. No circulating blasts
 - ii. Neutrophil count $<1.0 \times 10^9/L$, or
 - iii. Platelet count <100 x10⁹/L
 - b. Bone marrow aspirate and biopsy:
 - i. < 5% blasts
 - ii. No Auer rods
 - iii. No extramedullary leukemia
- 3. Partial remission:

Protocol: ARO-004

- a. All CR criteria if abnormal before treatment except:
- b. \geq 50 % reduction in bone marrow blast but still \geq 5% or
- c. Marrow blasts <5% with persistent Auer rods
- 4. Morphologic leukemia-free state:
 - a. Bone marrow: ≤5% myeloblasts
- 5. Hematologic Improvement (HI):

Hematologic response must be described by the number of positively affected cell lines.

- a. Erythroid response (E) (pretreatment Hgb <11 g/dL)
 - i. Hgb increase by ≥1.5 g/dL
- **b.** Platelet response (P) (pretreatment platelets $<100 \text{ x} 10^9/\text{L}$)
 - i. Absolute increase of $\ge 30 \times 10^9/L$ for patients starting with $> 20 \times 10^9/L$ platelets
 - ii. Increase from $< 20 \times 10^9/L$ to $> 20 \times 10^9/L$ and by at least 100%
- c. Neutrophil response (N) (pretreatment ANC $<1.0 \times 10^9/L$)
 - i. At least 100% increase and an absolute increase $> 0.5 \times 10^9/L$

10. Statistical Considerations

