1.1 Primary Objectives

- Overall response rate defined as Complete remission (CR) including incomplete blood count recovery (CRi)
- Duration of response

Protocol: ARO-004

• Progression-free survival

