Title of Study: A Phase II Study of Crenolanib Besylate in Subjects with Relapsed/Refractory Acute Myeloid Leukemia with FLT3 Activating Mutations

Number of Planned Subjects:

14 evaluable subjects

Length of Study: 3 years

Objectives:

Primary Objectives

- Overall response rate including Complete remission (CR) including incomplete blood count recovery (CRi)
- Duration of response
- Progression-free survival

Secondary Objectives:

- Safety and tolerability of crenolanib
- Pharmacokinetic analysis of crenolanib in patients with AML
- Analysis of phospho-FLT3 and other pharmacodynamic markers from serially collected circulating leukemic blasts and/or marrow blast samples
- Pharmacogenetic analyses, correlation of remission with genomic abnormalities including but not limited to mutant FLT3 allelic ratio
- Impact of crenolanib on hematological improvement, bridge to transplant, duration of leukemia control, blood and platelet transfusions, infections, days of hospitalization, performance status

Study Design:

Protocol: ARO-004

This is a Phase II open label study of crenolanib besylate. This study will enroll subjects with relapsed or refractory AML with FLT3 activating mutations. Prior treatment with other FLT3 TKIs is allowed. Subjects will take crenolanib 200mg/m²/day divided in three doses daily (preferably every eight hours), taken orally at least 30 minutes pre or post meal until disease progression, death, or the patient discontinues treatment for adverse events, investigator's judgment, or other reasons. Patients who are able to proceed to allogeneic stem cell transplant will be able to resume crenolanib therapy post-transplant in an attempt to maintain remission.

Diagnosis and Main Criteria for Inclusion and Exclusions:

Inclusion Criteria:

- Relapsed/refractory primary AML or AML secondary to antecedent hematologic disorder with an expected survival of 3 months or greater
- Patients must have tested positive for FLT3-ITD and /or other FLT3 activating mutations within < 60 days of the screening period.
- Age ≥18 years
- ECOG PS 0-2
- Adequate liver function, defined as total or direct bilirubin ≤1.5x ULN, ALT ≤3.0x ULN, AST ≤3.0x ULN. Exceptions for ALT and AST restrictions will be made in the setting of documented liver involvement with leukemia.
- Adequate renal function, defined as serum creatinine $\leq 1.5 x$ ULN
- Recovery from non-hematological toxicities of prior therapy (including HSCT) to no more than grade 1 (except alopecia)

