The modeling/simulation cycle described above was performed with combined data from two adult studies (19 patients, ARO-BRE-001 (NCT01229644) and 002 (NCT01243346)) and one pediatric study ARO-003 (NCT01393912). This data was used to perform distribution of the BSA-normalized crenolanib pharmacokinetic parameters and the expected distribution of BSA in an adult population to perform 1,000 Monte Carlo simulations for each regimen. In figure 8.1, the shaded regions represent the 95% CIs for each simulation. The patients' dosing interval is considered to be every eight hours. Although the drug would be administered three times a day on a "TID" schedule, it is important to understand that the simulation was performed using an every eight hour dosing schedule and every attempt should be made to dose the drug on this schedule.

[figure not shown]

Figure 8.1. The PK simulation for TID (median +/- SD) plotted based on a simulation of data from 19 adult patients and pediatric patients.

The serum PK results of the 16 AML patients enrolled to date at 100mg TID across two clinical studies show that fifteen have cycle 1 day 15 average trough levels of 444nM (standard error ±15nM), below the theoretical target of 680nM required to inhibit FLT3 signaling in bone marrow. In addition, the Pk data suggest that crenolanib is slowly absorbed with a t-max of 2-4 hours and mean terminal half-life ranging from 8.6-9.5 hours. This suggests the currently administered crenolanib dose of 100mg TID (protocol v3) is insufficient to achieve adequate sustained inhibition of FLT3 kinase activity. As of May 2013, of the 16 patients enrolled across two clinical studies, 4 have achieved a CR (1CR/3CRi) with 6 others having some short lived reduction in blast cells in either blood or marrow and another 4 patients showing no response. In the 6 patients with blast decrease, blast reduction occurred by 21 days but was not sustained. These results suggest pharmacologic failure for most patients at this initially selected dose of 300mg/day (100mg/TID). In addition, AML patients over 85kg did not achieve sustained responses and are potentially underdosed on a flat-dose schedule.

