10.1 Determination of Sample Size

The FLT3-3 D835 AML activating mutations have been refractory to currently available TKIs. An upper one-sided 75% confidence bound on the fraction of such patients who might respond to no treatment or ineffective therapy is 10%.

Therefore we will treat 15% response rate as our null hypothesis and submit 14 patients to this phase II trial. If at least 2 patients respond to treatment, the null hypothesis will be rejected. If the true response rate is 30%, this design will have 85.07% power and 8.61% type I error.

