10.3 Statistical and Analytical Plans

The primary end-point is overall response rate. We will use tests of the binomial proportion for both response and toxicity (Section 11). Descriptive statistics will be used for progression free survival and exploratory endpoints. Duration of response and PFS will be listed and additionally summarized using Kaplan-Meier methodology.

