10.3.6 Primary Outcome and Methodology

Response criteria will be adapted from the International Working Group for AML, as stated in section 9.1.

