10.3.7 Efficacy Analysis

The primary end-point is overall response rate (detailed in section 9.1). Descriptive statistics will be presented for all categories of each best response category. Duration of response and PFS will be listed and additionally summarized using Kaplan-Meier methodology. In addition, if at any time unacceptable toxicity is encountered in more than 33% of patients the accrual will stop and lower doses may be investigated.

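### Primary response rate is CR including CRi in section 1.1 but CR, CRi or PR in section 9.1, and section 10.1 does not say which one its 2-of-14 rule counts

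*Combined protocol and SAP*

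**What the plan says.** - **Section 1.1** gives the first primary objective as "Overall response rate defined as Complete remission (CR) including incomplete blood count recovery (CRi". PR is not mentioned.
- **The synopsis** words the same objective as "Overall response rate including Complete remission (CR) including incomplete blood count recovery (CRi". The word *including* does not close the list, so this line settles nothing.
- **Section 9.1** states who is a responder before it lists the criteria: relapsed/refractory patients on reinduction "who obtain a CR, CRi, or PR, with or without cytogenetic response, hematologic improvements, and morphologic leukemia-free state".
- **Section 10.3.6**, which is headed as the primary outcome and methodology, says only: "Response criteria will be adapted from the International Working Group for AML, as stated in section 9.1".
- **Section 10.3.7** says: "The primary end-point is overall response rate (detailed in section 9.1". It also plans descriptive statistics for every best-response category.
- **Section 10.3** says: "We will use tests of the binomial proportion for both response and toxicity". Response is not defined there.
- **Section 10.1** sets a 15% null and a 30% alternative with 14 patients, after quoting a 10% bound for patients on no or ineffective treatment. Its rule is: "If at least 2 patients respond to treatment, the null hypothesis will be rejected". It does not say what counts as responding.

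**The concern.** The objective and the analysis text lead to different primary endpoints. A patient whose best response is PR is a non-responder under 1.1 and a responder under 9.1, and no passage reconciles the two. With a cut-off of only 2 responders, the classification of a single patient can reverse the conclusion.

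The benchmark rates are affected as well. The 10%, 15% and 30% figures in 10.1 might describe CR/CRi or CR/CRi/PR. A reader cannot tell whether the null being tested belongs to the endpoint being counted.

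The trial is open label (8.8). A definition left open could in practice be chosen once the responses are known.

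**Working it through.** **1. The plan's own figures.** Let T(p) be the chance of at least 2 responders in 14 at true rate p:

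T(p) = 1 − (1 − p)^14 − 14·p·(1 − p)^13

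- T(0.15) = 1 − 0.1028 − 0.2539 = 0.6433
- T(0.30) = 1 − 0.0068 − 0.0407 = 0.9525

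Section 10.1 states 8.61% type I error and 85.07% power, so its figures are not reproduced. At least 2 responders in 10, with a null of 5% and an alternative of 30%, gives exactly 8.61% and 85.07%. That is a separate defect. The definition conflict does not depend on it, but the stated error rates cannot be used to judge how much the conflict matters.

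**2. The conflict without any assumption.** Take 14 patients with one CRi, one PR and no other response.

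| Definition | Responders | Rule (at least 2) |
|---|---|---|
| 1.1: CR or CRi | 1/14 | null not rejected |
| 9.1: CR, CRi or PR | 2/14 | null rejected |

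**3. How often the two would disagree.** Every CR/CRi responder is also a CR/CRi/PR responder. The decisions therefore differ exactly when there are fewer than 2 CR/CRi responders but at least 2 responders once PR is added:

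P(opposite decisions) = T(p + d) − T(p)

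Here p is the true CR/CRi rate and d is the rate of PR as best response. The documents give no value for d, so 5, 10 and 15 percentage points are assumptions. The values of p are the null (15%), the alternative (30%) and 25%, which is the 4 of 16 with CR or CRi reported in 8.6.

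Inputs: T(0.15) = 0.6433, T(0.20) = 0.8021, T(0.25) = 0.8990, T(0.30) = 0.9525, T(0.35) = 0.9795, T(0.40) = 0.9919, T(0.45) = 0.9971.

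| True CR/CRi rate | d = 5 points | d = 10 points | d = 15 points |
|---|---|---|---|
| 15% | 15.9% | 25.6% | 30.9% |
| 25% | 5.3% | 8.0% | 9.3% |
| 30% | 2.7% | 3.9% | 4.5% |

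Example: from 15% with d = 5 points, 0.8021 − 0.6433 = 0.1588.

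The figures fall as p rises because the cut-off of 2 is then usually met by CR/CRi alone.

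**4. The wording of 9.1.** The phrase after PR can be read in two ways. Hematologic improvement and morphologic leukemia-free state may be features that can accompany a CR, CRi or PR, or they may be further ways to qualify. On the second reading, one CRi plus one hematologic improvement would also reject the null. The table above uses the first reading.

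**The case against.** **Section 10 does point somewhere.** Section 10.3.7 sends the primary endpoint to 9.1, the only place that defines responders, and 10.1 uses the verb *respond*. A statistician working from section 10 would probably apply 9.1, and 1.1 would then be a narrower or outdated line. This is a fair account of how the conflict may have arisen. It does not remove it: 1.1 is worded as a definition of the primary objective, and 10.1 never states a response type for its rates.

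**All response categories will be tabulated.** That is true, and it lets a reader rebuild either rate. It does not say which rate the rejection rule uses.

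**The disagreement is rare if the drug works.** At CR/CRi rates of 25% to 30% the written rule gives opposite decisions in under 10% of trials for the PR increments shown. This stands. The larger figures belong to a true rate near the null.

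**Two stronger readings are tempting, and the documents do not support them.**

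- A reader might infer from 8.6 that 9.1 would raise the earlier response rate from 4/16 (25%) to as much as 10/16 (62.5%), because "4 have achieved a CR (1CR/3CRi) with 6 others having some short lived reduction in blast cells in either blood or marrow". That is not a valid upper bound. Section 8.6 lists a further 4 patients without response, so it accounts for 4 + 6 + 4 = 14 of 16 and leaves 2 unstated. Nor does it say whether any of the 6 met the PR criteria of 9.1. A short-lived fall in blasts is not the same thing.
- A reader might also infer from the marrow schedule in 7.2, 8.2 and Appendix IV, where later scheduled marrows depend on CR or CR/CRi being maintained, that the test is meant to count CR/CRi. The schedule does not show which definition the test uses. Marrows at the start of cycles 2 and 3 are scheduled regardless of response.

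**Conclusion.** The conflict is in the text, and it should be resolved before the primary analysis. Sections 1.1 and 9.1 classify a PR differently, the analysis section follows 9.1, and 10.1 is silent. That one CRi plus one PR in 14 reverses the decision rests on no assumption.

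How often this would happen cannot be known from the documents. Under the written 2-of-14 rule and assumed PR increments of 5 to 15 points, it is 16% to 31% from a 15% CR/CRi rate, 5% to 9% from 25%, and 2.7% to 4.5% from 30%. These are illustrations that take 9.1 to count CR, CRi and PR only. They do not show that the decision would usually turn on the definition, or that either definition is the one intended.

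**What to change.** Use one responder definition in 1.1, the synopsis, 9.1, 10.1 and 10.3.7. CR or CRi matches the objective as stated in 1.1. Suggested wording:

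> A responder for the primary endpoint is a patient whose best response is CR or CRi. PR, morphologic leukemia-free state and hematologic improvement are tabulated separately and do not count toward the decision rule.

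State in 10.1 that the null, the alternative and the cut-off refer to the chosen definition. Confirm that the 10%, 15% and 30% rates suit it. This is needed under either definition, because 10.1 gives no response type for any of them. If the sponsor means PR to count, change 1.1 instead, and say explicitly in 9.1 whether hematologic improvement and morphologic leukemia-free state count.

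No new data collection is needed, and the tabulation of every best-response category in 10.3.7 stays as planned. There are two costs. With CR/CRi the reported response rate may be lower. The change also touches a principal feature, so under 10.3.1 it needs an amendment, and it would be made in an open-label trial after some outcomes are known (8.6 reports them as of May 2013). The amendment should state this.

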1.2 Secondary Objectives

- Safety and tolerability of crenolanib
- Pharmacokinetic analysis of crenolanib in patients with AML
- Analysis of phospho-FLT3 and other pharmacodynamic markers from serially collected circulating leukemic blasts and/or marrow blast samples
- Pharmacogenetic analyses, correlation of remission with genomic abnormalities including but not limited to mutant FLT3 allelic ratio
- Impact of crenolanib on hematological improvement, bridge to transplant, duration of leukemia control, blood and platelet transfusions, infections, days of hospitalization, performance status

2. Sponsor Contact Information

Protocol Number:	ARO-004
Version	4.0
Version Date:	August 30 , 2013
Investigational Product:	Crenolanib
Development Phase:	II
Sponsor:	Arog Pharmaceuticals, LLC.
	[name]
	[name]
	Phone - [contact]
	Fax - [contact]
	Email - [contact]
Medical Monitor:	[name].
	M: [contact]
	F: [name]
	E-mail: [contact]
Project Manager	[name]
	O: [contact]
	M: [contact]
	F: [contact]
	E-mail: [contact]

3. Synopsis

Study Rationale

A number of FLT3 inhibitors with *in vitro* and *in vivo* activity against the FLT3 internal tandem duplication (ITD) mutation are in clinical development. These include midostaurin (PKC412, in phase III development), sorafenib (in phase III development), and quizartinib (AC220, in phase II development).

However, most AML patients who initially respond to these FLT3 tyrosine kinase inhibitors (TKIs) relapse. One of the mechanisms of resistance to FLT3 inhibitors is the development of secondary mutations in the FLT3 tyrosine kinase domain (TKD). The most common secondary TKD mutations that have been identified are substitutions of aspartic acid at the position 835 of FLT3 (D835Y/V). The D835 substitution mutation in FLT3 results in ligand-independent constitutive phosphorylation of the tyrosine residues present in the kinase domains of FLT3 protein. This mutation is resistant to midostaurin, sorafenib and even quizartinib. Thus, there exists a need to develop FLT3 inhibitors with the ability to inhibit FLT3-D835 signaling to treat patients with relapsed AML.

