7.3 Supportive Care Guidelines

Supportive measures including blood and platelet transfusions, antimicrobials, etc. are permitted. The administration of hematopoietic colony stimulating factors is not permitted.

Other chemotherapy, investigational cytotoxic agents, radiation, or biologic therapy is prohibited while the subject is on study with the following exceptions during cycle 1:

- 1. During the first 5 days of cycle 1 of study only, subjects may receive leukapheresis (not more than three procedures per week and not more than five procedures in total) to control elevated blast and/or platelet counts
- 2. hydroxyurea (up to a maximum of 5 gm /day) for a maximum of 14 days may be administered during cycle 1.
- 3. Leukapheresis and hydroxyurea may be administered together according to the guidelines above.

8. Study Procedures

After providing informed consent, if meeting the screening inclusion/exclusion criteria, and after having baseline evaluations performed within 28 days prior to first dose of study drug patients will be enrolled in the study.

The following assessments will be performed after completion of the informed consent and within 28 days of start of study drug except as otherwise specified:

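### As written, the hematologic improvement rule can credit a red-cell or platelet transfusion as improvement in two of its three cell lines

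*Combined protocol and SAP*

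**What the plan says.** Section 9.1 item 5 defines hematologic improvement by cell line, each relative to the pretreatment count.

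- **Erythroid:** the line applies to patients described by "Erythroid response (E) (pretreatment Hgb <11 g/dL", and the requirement is "Hgb increase by ≥1.5 g/dL".
- **Platelet:** the line applies when the pretreatment count is below 100 x10^9/L. Patients starting above 20 need an absolute rise of at least 30. Patients starting below 20 must pass 20 and at least double.
- **Neutrophil:** the line applies when the pretreatment count is below 1.0 x10^9/L. It requires "At least 100% increase and an absolute increase" of more than 0.5 x10^9/L.

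The only further instruction is that "Hematologic response must be described by the number of positively affected cell lines". Section 7.3 states that "Supportive measures including blood and platelet transfusions, antimicrobials, etc. are permitted", and it prohibits colony stimulating factors.

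Section 1.2 makes this a secondary objective: "Impact of crenolanib on hematological improvement, bridge to transplant". The same bullet also lists blood and platelet transfusions. Section 10 gives no rule, test or threshold for hematologic improvement.

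**The concern.** The erythroid and platelet rules look only at the size of a rise. Nothing tells the analyst to set aside a count lifted by a transfusion, or to ask whether the rise lasted. The patients who can qualify are those with low haemoglobin or platelets, and section 8.7.2 says that abnormal counts at the start and myelosuppression during therapy are expected. They are therefore plausible candidates for transfusion.

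At stake is the meaning of a named secondary result in a trial without a comparator. More transfusion, which is an unfavourable sign, could raise the reported improvement rate, and there is no control rate against which to see the inflation. Two analysts could also derive different rates from the same data, depending on how each handled post-transfusion counts.

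**Working it through.** The plan states no improvement rate, so there is no figure to reproduce. The check is of the text, followed by arithmetic on assumed increments.

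1. **Is the missing condition supplied elsewhere?** Outside section 9.1, transfusion is mentioned in the objectives (section 1.2 and the Synopsis), the background (section 5.5.4), supportive care (section 7.3) and the examples of serious events (Appendix VII). None of these limits how improvement is scored. Section 10 adds nothing on it.

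2. **Erythroid line.** Threshold: 1.5 g/dL (section 9.1). Assumed rise per red-cell unit: 0.7 to 1.3 g/dL.
   - One unit: 0.7 to 1.3, below 1.5 throughout.
   - Two units: 2 x 0.7 = 1.4 to 2 x 1.3 = 2.6. The rule is met once the rise per unit reaches 1.5 / 2 = 0.75.

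3. **Platelet line, starting below 20 x10^9/L.** Assumed rise per transfusion: 15 to 40.
   - From 9: 9 + 15 = 24 to 9 + 40 = 49. Doubling needs 2 x 9 = 18 and the count must pass 20, so the rule is met across the range.
   - In general, a start b with rise d qualifies if b + d > 20 and b + d ≥ 2b. At d = 15 this needs b above 5 and at most 15. At d of 20 or more, every start above 0 and below 20 qualifies.

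4. **Platelet line, starting above 20.** The rise must be at least 30. Assumed increments of 30 to 40 meet the rule; those from 15 to just under 30 do not.

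5. **Neutrophil line.** Red-cell and platelet transfusions are not expected to move it, and growth factors are prohibited. It also lacks a confirming count, but the transfusion problem does not apply.

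6. **Opportunities to qualify.** Section 8.2 schedules about 4 counts in weeks 1 and 2, 2 in weeks 3 and 4, and 2 in cycle 2, so about 8 in two cycles. If each had an independent chance q of being lifted over the threshold by a recent transfusion, the chance of at least one false improvement would be 1 - (1 - q)^8:

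| Assumed q | 1 - (1 - q)^8 |
|---|---|
| 5% | 34% |
| 10% | 57% |
| 20% | 83% |

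   Neither q nor independence comes from the documents. The table shows only how repeated looks add up when no confirmation is required.

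7. **Pretreatment count.** The bias can also run downward. A patient at 10 g/dL given two units at the low end would have a pretreatment value of 10 + 1.4 = 11.4. That is above the 11 g/dL limit, so the patient leaves the erythroid category.

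**The case against.** Four points can fairly be made on the other side.

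- **The sufficiency of one count is inferred from silence.** Section 9.1 does not say that one count is enough. It describes its criteria as adapted from a cited working-group standard and given in brief, so the source may carry further conditions. This stands as a caution. But section 9.1 imports no such condition, and an analyst working from this plan has none to apply.
- **A transfusion does not always score.** This is correct. One red-cell unit falls short on the assumed range, two units fall short at its low end, and a platelet rise under 30 fails for patients starting above 20. The claim is that a transfusion can score.
- **The stakes are limited.** Improvement is one item in a multi-part secondary objective with no test or decision attached. Transfusion use is reported under the same objective, so a reader would have some warning. This stands, and it sets the weight of the point.
- **Confirmation must fit the schedule.** Counts are twice weekly in weeks 1 and 2, so a requirement that consecutive counts be 7 days apart would often fail there. The fix has to allow for this.

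A reader might go further and infer that two transfused patients of 14 could reach the rejection threshold in section 10.1, because the responder sentence in section 9.1 mentions hematologic improvement. The documents do not support that. The sentence requires CR, CRi or PR, "with or without cytogenetic response, hematologic improvements, and morphologic leukemia-free state", so improvement is neither needed nor sufficient. Section 1.1 and the Synopsis define the primary rate as CR including CRi.

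**Conclusion.** The point holds for the erythroid and platelet lines. Applied as written, the rule can count the effect of a transfusion as improvement on study drug, and a transfused pretreatment value can hide real improvement. The net direction is not certain, although the many chances to qualify on a single count push it upward.

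The size cannot be fixed from the documents. The illustrations rest on assumed increments of 0.7 to 1.3 g/dL per red-cell unit and 15 to 40 x10^9/L per platelet transfusion. How often patients would be transfused near a scheduled count is unknown.

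The effect is confined to a descriptive secondary measure; the primary CR/CRi rate and the section 10.1 decision rule are not affected. The correction should be made before analysis, because without it the improvement rate cannot be read as drug effect.

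**What to change.** Amend section 9.1 item 5 for the erythroid and platelet lines:

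- Exclude any count, pretreatment or on-study, that falls within a window after a transfusion of the relevant product. Fix the window before analysis; 14 days for red cells and 7 days for platelets are examples, not values from the documents.
- Require the rise to be confirmed on a later scheduled count at least 7 days after the first qualifying one. It need not be the next count, so the rule works with the twice-weekly counts of weeks 1 and 2.
- Count patients with no evaluable transfusion-free count as not improved, and keep them in the denominator.

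The derivation can use the transfusion records needed for the existing transfusion objective. Section 8.9 has supportive therapy documented as concomitant medication, and Appendix IV collects non-drug therapies. The sponsor should first confirm that the CRF captures transfusion dates and product.

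The cost is one added derivation and a lower reported improvement rate. From cycle 3, when section 8.2 has counts monthly, confirmation may take several weeks, and heavily transfused patients will count as not improved. The change concerns analysis only and does not alter transfusion practice.
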